To ensure concealment, the primary investigator, assessors and administrators of the randomisation were blinded to the block sizes, as the randomisation code was stored in REDCap, with no access for the project group.

Sample size and power considerations

The sample size and power estimation were based on the expected between-group difference in the change in SPADI score from baseline to the 12 weeks follow-up. In order to achieve an *a priori* statistical power of at least 85%, with a two-sided significance level $\alpha=0.05$, with an anticipated standard deviation (SD)=15.41 SPADI units (5), the estimated total sample size was n=130 (~ 65 participants in each group), to be able to detect a minimal clinically relevant difference defined as 8 points on the SPADI-score (6,7).

[figure not shown]
Correction:

In the study protocol we estimated an eligible population of approximately n=384 women willing to participate (<https://doi.org/10.1186/s13063-022-06659-1>), based on the cross sectional survey sent to

Individualised treatment vs. a home-based exercise program in women with late-term shoulder impairments after primary breast cancer surgery

approximately 4.300 women in Region of Southern Denmark, corresponding to an expected eligible population rate of 8%.

In fact, we sent out the questionnaire to 9.934 women nationwide, and obtained a participation rate of 56.7% in the cross sectional survey. For the Region of Southern Denmark we received 1.164 complete replies. Of these only 129 women matched the inclusion and exclusion criteria, and furthermore, 76% of these eligible women declined the offer to participate, resulting in $n=31$, corresponding to a much lower than expected, eligible population rate of 2.66%.

Statistical interim analysis and early stopping rules

No statistical interim analyses were planned or done. Patient recruitment stops when a total number of 130 patients have been included and finished their intervention or when the deadline August 31, 2022 is reached.

Timing of final analysis

The final analysis for the between group comparison (*Intervention group vs. Control comparator group*) for the primary endpoint (baseline, 4-, 8- and 12-weeks follow-up) is planned to be performed after the last randomised patient has completed the 12 weeks follow-up. The publication of the trial will be prepared when the data have been received and cleaned (anticipated by April 2023).

Timing of outcome assessments

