The reason for each crossover or withdrawal will be registered. Participants performing a crossover will remain in the study and be analysed following the intention-to-treat principle (i.e., remaining in their original group). The level of consent withdrawal will be classified as:

1. consent to continue follow-up and data collection;
2. consent to continue data collection only; or
3. complete withdrawal with no further follow-up and data collection (13).

In the CONSORT Flow Diagram numbers and reasons for withdrawal and/or loss to follow-up will be presented given at the 4-, 8- and 12-weeks (primary end point) outcome assessment; separately for the two intervention groups.

Baseline characteristics

The following data will be used to describe patients by randomisation group at baseline: mean age, height, weight, body mass index (BMI), smoking, alcohol consumption, highest education level, employment, index shoulder, dominant side affected, duration of shoulder symptoms, pain medication consumption due to shoulder related pain, depression, anxiety and outcome measures will be collected at baseline. The baseline characteristics are illustrated in [Table 1](#).

Categorical variables will be calculated and presented in numbers and percentages. While Means and Standard Deviations (SDs) will be calculated and presented for continuous variables if data follows a normal distribution; in case, continuous variables does not appear to follow normal distribution, median and interquartile range will be calculated. No tests of statistical significance will be conducted for baseline characteristics.

ANALYSIS

Primary outcome

Shoulder Pain and Disability Index (SPADI) [Time Frame: 0, 4, 8 and 12 weeks]

The primary outcome measure will be the between-group difference in change in SPADI-score ($\Delta\text{SPADI}_{12} = \text{SPADI}_{12\text{-weeks follow-up}} - \text{SPADI}_{\text{baseline}}$) from baseline to 12 weeks after initiating the treatment. SPADI is considered a valid, reliable, and responsive patient-reported questionnaire assessing shoulder pain and function, where each domain score is equally weighted and added to a total percentage score that ranges from 0 (best) to 100 (worst) (9,14) ([Figure 2](#)).

Key secondary outcomes

- *SPADI pain [Time Frame: 0, 4, 8 and 12 weeks]*

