A key secondary outcome will be the between-group difference in change in shoulder pain during sleep (Δ Pain during sleep₁₂ = Pain during sleep_{12-weeks follow-up} – Pain during sleep_{baseline}) from baseline to 12 weeks after initiating the treatment. The NRS is a valid, reliable and responsible single 11-item patient-reported pain scale that ranges from 0 (no pain) to 10 (worst pain) (22).

- *Shoulder pain during flexion/rotation/abduction [Time Frame: 0 and 12 weeks]*

A key secondary outcome will be the between-group difference in change in shoulder pain during flexion/rotation/abduction (Δ Pain during flex rot abd₁₂ = Pain during flex rot abd_{12-weeks follow-up} – Pain during flex rot abd_{baseline}) from baseline to 12 weeks after initiating the treatment. The NRS is a valid, reliable and responsible single 11-item patient-reported pain scale that ranges from 0 (no pain) to 10 (worst pain) (22).

The primary and key secondary outcomes will be presented as illustrated in **Table 2**.

Analysis methods

The CONSORT guideline (13) will be followed for all trial reporting aspects, as recommended by the “*Enhancing the QUAlity and Transparency Of health Research*” (EQUATOR) network website (23).

The primary (continuous) outcome will be analysed by using repeated measures mixed effects models, including participants as a random effect, with fixed effect factors for group (2 levels) and week (4 levels for the SPADI questionnaire [weeks 0, 4, 8, and 12]), the stratification factors and the interaction between group and week, adjusted for baseline values. To assess the adequacy of the linear models describing the observed data—and checking assumptions for the systematic and the random parts of the models—the model features will be investigated via the predicted values and the studentized residuals; that is, the residuals have to be normally distributed (around 0) and be independent of the predicted values. Results will be expressed based on least squares mean estimates with standard errors (SE) as well as the differences in the least squares means with 95% CIs to represent precision of the contrast between groups. Further, for the primary

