Outcome	12 weeks after initiating the treatment		Between-Group Difference in Mean Improvement	
	Intervention Group	Control Comparator Group	Difference in LSMeans (95%CI)	P-Value
	Mean	SE	Mean	SE
Primary endpoint				
Change SPADI score — 0 to 100				
Key secondary outcome measures				
Change SPADI pain (0-10)				
Change SPADI function (0-10)				
Change Clinical response (SPADI change score)				
GPE impression of the treatment success (0-7)				
Change A-ROM in the affected shoulder (degree)				
Change P-ROM in the affected shoulder (degree)				
Number of treatments received due to shoulder symptoms (mean)				
NRS maximum shoulder pain intensity (0-10)				
NRS shoulder pain during general activities (0-10)				
NRS shoulder pain at rest (0-10)				
NRS shoulder pain during sleep (0-10)				
NRS shoulder pain assessment during flexion/rotation/abduction (0-10)				
Response to Treatment				
SPADI minimal important change criteria† no. (%)				

* All analyses will be based on the Intention-To-Treat (ITT) population: Using Repeated-Measures, Mixed Models (with no simple imputation for missing data); Estimates will be least squares means (LSMeans) and Standard Errors (SE) with the difference between groups reported with 95% Confidence Intervals (CI).

† Patients will be classified as having a clinically relevant change if the SPADI score improves by 8 points or more; missing data will be replaced by single-step non responder imputation.

Table 3: Serious Adverse Events at 12 weeks in the ITT population*

	Intervention Group	Control Comparator Group
Serious Adverse Event (SAE) - no (%)		
Musculoskeletal		
Deep infection, no. (%)		
Shoulder dislocation, no. (%)		
Shoulder fracture, no. (%)		
Cardiovascular		
Vascular injury (arterial and venous damage), no. (%)		
Pulmonary embolism, no. (%)		
Deep venous thrombosis, no. (%)		
Acute myocardial infarction, no. (%)		
Nervous system		
Nerve injury, no. (%)		
Deaths, no. (%)		
Discontinuation due to AE(s) — no. (%)		

* This table includes all Serious Adverse Events (SAE's) that occurred during the 12 weeks study period, but not necessarily a causal relationship with the treatment administered. An adverse event was classified as serious if it was fatal or life-threatening, required or prolonged inpatient hospitalisation, was disabling, resulted in (a congenital anomaly or birth defect), or required medical or surgical intervention to prevent permanent impairment or damage.

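### The primary mixed model uses week-0 SPADI as both response and covariate and leaves the tested contrast open: one reading tests at about 7.5–8.5% instead of 5%, the other makes the baseline adjustment inert

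*SAP*

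**What the plan says.** In Analysis methods, the primary outcome is analysed by a repeated-measures mixed model "with fixed effect factors for group (2 levels) and week (4 levels for the SPADI questionnaire [weeks 0, 4, 8, and 12". Strata also enter as fixed effects, and the description ends on "the interaction between group and week, adjusted for baseline values". The random part of the model is given only as "including participants as a random effect": no further covariance is stated, and there is no baseline-by-week term. Results are reported as "differences in the least squares means with 95% CIs to represent precision of the contrast between groups", without saying at which week or between which weeks.

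The endpoint is defined elsewhere as a change. Under Primary outcome, "The primary outcome measure will be the between-group difference in change in SPADI-score", with a formula subtracting baseline from week 12. Table 2 heads the comparison "Between-Group Difference in Mean Improvement" but fills it with a difference in least squares means. The sample size is "based on the expected between-group difference in the change in SPADI score from baseline to the 12 weeks follow-up" and was computed "with an anticipated standard deviation (SD)=15.41 SPADI units"; the SAP does not say outright whether that SD belongs to the change or to a single visit.

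**The concern.** A baseline-adjusted repeated-measures model normally has only post-baseline visits as responses. Here week 0 is a response too. At week 0 the covariate equals the response, so its slope is exactly 1; at later visits the slope is below 1. The model has one common slope and, under a random intercept, one common variance. The week-0 rows are nearly determined by the covariate, so they pull the pooled variance down, and the week-12 comparison inherits a variance that is too small.

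Two contrasts fit the text:

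- **Reading 1:** the difference in least squares means at week 12.
- **Reading 2:** the group difference in week 12 minus week 0, which is closer to the formula under Primary outcome.

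Two analysts could follow the SAP and report different estimates and P-values. At stake are the standard error, confidence interval and test of the primary result. The same interval also decides the SAP's rule that excluding differences above 4 points shows no clinically meaningful difference.

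**Working it through.** **Inputs.** From the SAP: two-sided alpha 0.05, difference 8, SD 15.41, 65 per group, visits at weeks 0, 4, 8 and 12, participant random effect. Assumed, because the SAP gives no value: complete data and equal between-visit correlation r = 0.3, 0.5, 0.7, with unit variance at each visit. The standard-error ratios and error rates do not depend on the SD.

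**The plan's own figure.** Total n = 4 × [15.41 × (1.960 + 1.036)/8]² = 133.3, or 67 per group after rounding up. At 65 per group, power is Φ(8/(15.41√(2/65)) − 1.96) = 84.1%. The stated 130 and 85% are reproduced closely, though marginally short.

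**Reading 1, week-12 difference.**

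1. The covariate is constant within a woman, so its slope is that of her four-visit mean on baseline: b = (1 + 3r)/4.
2. The residual variance is (1 − b)² at week 0 and 1 − 2br + b² at each later visit. The latter is the true variance behind the week-12 contrast.
3. The model uses the average over the four visits, which simplifies to 1 − b².
4. Actual error = 2 × [1 − Φ(1.96 × √(model/true))].

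| r | b | Week-0 variance | True week-12 variance | Model variance | SE ratio | Error |
|---|---|---|---|---|---|---|
| 0.3 | 0.475 | 0.276 | 0.941 | 0.774 | 0.907 | 7.5% |
| 0.5 | 0.625 | 0.141 | 0.766 | 0.609 | 0.892 | 8.0% |
| 0.7 | 0.775 | 0.051 | 0.516 | 0.399 | 0.880 | 8.5% |

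Simulation with the five strata (20,000 null trials per r) gave 7.6/8.0/8.5%, and 7.6/8.0/8.9% with 30 per group. Satterthwaite degrees of freedom do not cure it: 7.5/7.7/8.2% in 10,000 trials. With first-order autoregressive correlation, simulated error was 8.5/9.6/11.9%. The point estimate is unbiased. The same model restricted to weeks 4, 8 and 12 gave 5.1/5.1/5.2%.

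**Reading 2, week 12 minus week 0.** The covariate enters both weeks with the same coefficient and cancels. In one test data set the estimate was 1.248 with SE 2.681, with and without it. Simulated error was 5.3/5.0/5.1%. The variance of a change is 2(1 − r), against 1 − r² for ANCOVA, so the SE ratio is √(2/(1 + r)) = 1.240/1.155/1.085. That is the precision of an adjusted analysis on (1 + r)/2 = 65/75/85% of the women. Simulated power for 8 points:

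| 15.41 is the SD of | Reading 2 (r = 0.3/0.5/0.7) | Week-12 ANCOVA |
|---|---|---|
| change | 83/84/84% | 94/92/88% |
| each visit | 70/84/97% | 86/92/98% |

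The 5% also needs equal correlation. With autoregressive correlation 0.5, the average of the six between-visit correlations is (3×0.5 + 2×0.25 + 0.125)/6 = 0.354. The model then uses 2 × 0.646 for a change whose variance is 2 × (1 − 0.125) = 2 × 0.875. The SE ratio is √(0.646/0.875) = 0.859 and the error about 9.2%.

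**Alternative ways of fitting it.** Taking change scores as the response with week 0 kept shifts the covariate coefficient by 1 and leaves the fit unchanged (week-12 difference −0.599, SE 2.168 either way in the test data set). With an unstructured covariance, slope 1 fits week 0 exactly and the likelihood has no maximum: at slopes 0.9, 0.99, 0.999 and 0.9999 the profile log-likelihood was −1760.9, −1461.5, −1162.2 and −862.9, a gain of 130 × ln 10 = 299.3 per step.

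**Outcomes measured only at weeks 0 and 12**, if given the same model. Here b = (1 + r)/2 and the model variance is (1 − r)(3 + r)/4. Reading 1 has SE ratio 0.748/0.734/0.722 and error 14.3/15.0/15.7% (simulated 13.7/15.3/15.6%). Under reading 2 the random-intercept variance falls to zero, so the covariate does not cancel. The SE ratio is √((3 + r)/4) = 0.908/0.935/0.962 and simulated error is 7.6/6.8/6.2%. ANCOVA gave 4.9/5.3/5.2%.

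**The case against.** The best defence is that reading 2 is the intended one. The endpoint formula, the sample-size basis and the Table 2 row all speak of change. On that reading the error is near 5% under equal correlation and, if 15.41 is the SD of change, power stays near the planned level. The SAP never promises ANCOVA precision, so a redundant covariate is inefficiency, not error. This has force: the inflation belongs to reading 1 only, and reading 2 need not fall short of planned power. But the SAP reports differences in least squares means and explicitly adjusts for baseline. Nothing rules reading 1 out, and under reading 2 the stated adjustment does nothing.

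Several qualifications also stand:

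- The 7.5–8.5% range rests on assumed equal correlations and is not an upper bound.
- Exact cancellation under reading 2 needs complete data and a positive random-intercept variance. With 15% dropout and r = 0.5, the SE with the covariate was 0.986 of that without.
- The effect on the 4-point rule is mostly small. At no true difference, the chance that the interval lies within ±4 rose by at most 2.2 percentage points over ANCOVA in five of six settings. The exception is r = 0.7 with 15.41 as the visit SD: 24.7% against 7.9%.
- The two readings disagree at the 0.05 level in about 5% of null trials, but a change analysis and a valid ANCOVA disagree nearly as often. That supports naming the contrast; it does not measure the double use of baseline.

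The planned residual checks might reveal the misfit, but no fallback is specified, so any repair would be chosen with the data in view.

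**Conclusion.** The concern holds and should be corrected before the primary analysis. As written, the model puts week-0 SPADI on both sides and leaves the contrast open. If the week-12 difference from a random-intercept fit is tested, the true two-sided error is about 7.5–8.5% for equal correlations of 0.3–0.7, and roughly 8–12% if correlation decays over time. The interval is too narrow by the same 9–12% as the standard error under equal correlation. If week 12 minus week 0 is tested, size is about right under equal correlation, but the adjustment is inert and the standard error is 8–24% larger than it need be. That lost precision could matter, because recruitment may stop on 31 August 2022 short of 130.

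The nine continuous key secondary outcomes with a baseline value are affected only if they receive the same model, as the abstract, Table 2 and the Appendix Table 1 footnote suggest. Global perceived effect and number of treatments have no baseline value and are not affected.

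**What to change.** Name the group difference at week 12 as the primary contrast, use baseline once, and state the covariance. Either of these does it:

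- **Option A:** responses at weeks 4, 8 and 12; fixed effects for baseline, baseline-by-week, group, week, group-by-week and stratum; unstructured within-woman covariance.
- **Option B:** keep week 0 as a response, drop the baseline covariate, constrain both groups to a common week-0 mean, and use an unstructured covariance.

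For active and passive range of motion and pain during flexion/rotation/abduction, use a week-12 ANCOVA with baseline and stratum. State that global perceived effect and number of treatments are analysed without a baseline covariate.

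The cost is SAP wording and a few lines of code, with no new data. Option A loses women with no post-baseline value; Option B keeps everyone in the Full Analysis Set, which the SAP defines by a measured baseline.

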This trial is designed as a stratified (by type of surgery and radiotherapy), block randomised (1:1 allocation), controlled, parallel group and assessor-blinded, single-centre superiority trial conducted in Denmark. Women are recruited from an earlier letter inquiry, based on a register extract, including an invitation to participate in a cross-sectional survey of late-term effects. Women reported shoulder impairments invited to participate in this trial and randomised to an expert assessment of shoulder impairments with an individualised treatment plan or to a 12 week home-based program, which is a minimal intervention within the physiotherapeutic rehabilitation and is delivered in a pamphlet. The two interventions are more described specifically in the trial protocol. The primary endpoint will be assessed at the 12 weeks follow-up, while many of the outcome measures are also collected at 4 and 8 weeks follow-up.

The SAP is reported in accordance with the “*Guidelines for the Content of Statistical Analysis Plans in Clinical Trials*” (2). The trial was registered prior to First Patient First Visit at ClinicalTrials.gov (NCT05277909) and follow the principles of the Declaration of Helsinki (3). The recruitment period started in April 2022 (i.e. First Patient First Visit), and expected to be completed in August 2022 (i.e. Last Patient First Visit).

Randomisation, allocation concealment, and blinding

Eligible participants were randomly assigned in permuted blocks of 2 to 6, with a 1:1 allocation, based on a computer-generated randomisation list generated by an independent data manager implemented into the REDCap randomisation system (4), to either *Intervention group* or *Control group*. Participants were stratified in 5 groups according to type of surgery and +/- radiotherapy treatment:

1. Breast Conserving Surgery (BCS) and Sentinel Lymph Node Dissection (SLND) + radiotherapy;
2. BCS and SLND – radiotherapy;
3. BCS and Axillary Lymph Node Dissection (ALND) + radiotherapy;
4. Mastectomy and SLND – radiotherapy; and
5. Mastectomy and ALND + radiotherapy)

Immediately after obtaining the written informed consent, the baseline measures and outcomes will be collected. The outcome assessors who performed the clinical baseline assessment will also perform the 12-week follow-up, blinded towards treatment allocation. Participants were informed about their group allocation directly after randomisation.

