outcome, a 95% CI excluding differences greater than 4 SPADI points between groups will be interpreted as indicating absence of a clinically meaningful difference. Dichotomous outcome variables will be analysed with logistic regression, with identical fixed effect factors and covariates as the mixed linear model described above. Missing data for dichotomous outcomes will be computed based on conservative (non-responder) imputations.

Subgroup analyses (24) will be used to examine whether the observed overall treatment effect varies across participants subgroups, and to whether the effect is modified by the value of a variable assessed at baseline, analysed by the following thresholds: median age, median duration of shoulder symptoms, obesity ($BMI \geq 30 \text{ kg/m}^2$), dominant side affected (left vs right). This statistical approach to evaluate potential effect modifiers, will be a test for statistical interaction whether the treatment effect (net benefit on change in the SPADI score) varies across levels of the effect modifier (25).

Missing data and sensitivity analyses

To handle missing data, repeated-measures linear mixed effects models will be used (26-29). These models are considered valid if data are “*Missing at Random*” (i.e., any systematic difference between the missing values and the observed values can be explained by differences in observed data) (30).

The following four strategies for handling and interpretation of missing data will be applied in the sensitivity analysis:

1. We will attempt to follow up all randomised participants, even if they withdraw from allocated treatment (i.e., contact all individuals unless they explicitly stated that they had withdrawn their consent);
2. Perform a main analysis of all observed data that are valid under a plausible assumption about the missing data (i.e., data as randomised; using linear mixed effects models, assuming that data are “*Missing at Random*”);
3. Perform sensitivity analyses to explore the effect of departures from the assumption made in the main analysis (i.e., non-responder-imputation: using the value at baseline to replace missing data);

these models will be informative about the robustness in case data are “*Missing Not At Random*”); and

4. Account for all randomised participants, at least in the sensitivity analyses (including strategy 2 and 3, plus the corresponding analyses based on the per protocol population) (28).

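### Age and symptom duration are cut at the sample median for the interaction tests; keeping them continuous would recover some power at almost no cost, if effect modification is roughly linear

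*SAP*

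**What the plan says.** Under Analysis methods, the SAP plans subgroup analyses of the SPADI treatment effect, "analysed by the following thresholds: median age, median duration of shoulder symptoms", then BMI of 30 or more and dominant side. Inference is by a formal interaction test of whether the benefit on SPADI change differs between the levels of each modifier. The median cuts therefore define the variables that enter the formal test, and not only how results are shown.

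The SAP's Table 1 shell lists mean age and duration of shoulder symptoms in years. The SAP plans no analysis of either as a continuous modifier, gives no reason for the median, and gives no power for any interaction test. The short section on additional analyses adds nothing for the primary outcome. The trial is sized only for the overall comparison, to detect a "minimal clinically relevant difference defined as 8 points on the SPADI-score".

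**The concern.** A median split treats all women on one side of the cut as alike, and treats two women just either side of it as different. When the treatment effect changes gradually with age or duration, that throws away information already collected. The test for interaction does not need a cut.

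Interaction tests in a trial sized for its main effect are weak to begin with. An avoidable further loss makes it more likely that real effect modification goes undetected, and that a non-significant result is read as evidence of a uniform effect. The median is also known only once recruitment is complete and has no clinical meaning, so the resulting subgroups are hard to carry over to another trial.

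**Working it through.** **Inputs.** From the SAP, Sample size and power considerations: total n=130 (65 per group), SD 15.41, difference 8 points, two-sided alpha 0.05, power at least 85%. From Trial design: 1:1 allocation. The SAP gives no distribution for age or symptom duration, so a range of shapes is assumed. SD 15.41 is taken as the residual SD.

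**1. The plan's own figure.** The SE of the overall difference is 15.41 × √(2/65) = 2.70. Power ≈ Φ(8/2.70 − 1.96) = Φ(1.00) = 84%. This reproduces the stated 85% to within about a point. Reaching 85% by the same formula takes 67 per group.

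**2. Information kept by a median split.** Under a linear group × modifier interaction, the split keeps a fraction equal to the squared correlation between the modifier X and the indicator X > median:

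| Assumed shape | Information kept | Lost | Effective n out of 130 |
|---|---|---|---|
| Uniform | 0.75 | 25% | 98 |
| Normal | 2/π = 0.637 | 36% | 83 |
| Exponential (strong skew) | (ln 2)² = 0.48 | 52% | 62 |

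For age, a normal shape with assumed mean 60 and SD 10, cut off at 21 and 78, keeps 0.656.

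For duration, the inclusion criteria require surgery within the last 3–7 years. If symptoms began after surgery, duration is at most about 7 years. Under that cap the fraction kept is:
- 0.75 if duration is uniform;
- 0.69 if onset is uniform between surgery and now;
- 0.65 or 0.585 for an exponential truncated at 7 years, with mean 3 or 2 years before truncation;
- 0.49 only when that mean is as short as 1 year.

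**3. Power of the split interaction test.** With four equal cells of 32.5 women, SE = 15.41 × √(4/32.5) = 5.41, twice the SE of the overall difference. For an 8-point difference in treatment effect between the halves, z = 8/5.41 = 1.48. Power = Φ(1.48 − 1.96) = 32%, the other tail being negligible. The difference detectable with 80% power is 2.80 × 5.41 ≈ 15 points.

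**4. Power with the modifier continuous.** Take the same linear interaction, with its slope set so that the halves differ by 8 points. Dividing z by the square root of the fraction kept gives:
- uniform: 1.48/√0.75 = 1.71, power Φ(1.71 − 1.96) = 40%;
- normal: 1.48/√0.637 = 1.85, power Φ(1.85 − 1.96) = 46%.

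On the between-halves scale, the differences detectable with 80% power become 15.1 × √0.75 ≈ 13 and 15.1 × √0.637 ≈ 12 points.

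**5. Simulation check.** Least-squares fits with a group × modifier term at n=130 gave 31% (split) against 40% (continuous) for a uniform modifier, and 29% against 43% for a normal one. Direction and approximate size agree with steps 3 and 4.

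**6. A smaller sample.** The SAP reports recruitment far below expectation and a deadline that could end it before 130. At n=31, the yield the SAP reports for one region and used here only as an illustration, the formulas give 11% with the split and 13–15% with a continuous modifier.

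**The case against.** The strongest reply is that nothing in the plan is wrong. The modifiers, the rule for the cut and a formal interaction test are all prespecified. A median rule also prevents anyone from choosing a favourable cut after seeing results. That the median depends on who was recruited affects how subgroups are described, and does not make the test invalid. This stands: the point is about efficiency. A prespecified continuous term, however, protects equally well against a chosen cut.

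The loss is also conditional. It assumes roughly linear modification and an assumed distribution, and a true step at the median would lose nothing. A reader might infer that half the information is thrown away. The SAP does not support that as a general statement: it needs strong skew, which the surgery window makes less likely if symptoms began after surgery.

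A reader might also infer that a well-powered test is being spoiled, for example one falling from 80% to 61% or 68% power. This trial has no such test. The weakness comes mainly from sample size, and the continuous version would still miss an 8-point interaction more often than not under a uniform or normal shape.

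Finally, no decision rests on these tests. The SAP has no rule turning a non-significant interaction into a claim of no effect modification, and its result-table shells contain no subgroup results. That limits the weight of the point but does not remove the case for a nearly free gain.

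**Conclusion.** The point holds as a cheap improvement. Under roughly linear modification, the median split costs about 25% (uniform) to 36% (normal) of the information on effect modification by age and symptom duration, and more if duration is strongly skewed. At n=130 and SD 15.41, avoiding it raises power for an 8-point interaction from about 32% to about 40–46%.

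These figures rest on the assumed shapes and on 15.41 as the residual SD. Baseline adjustment and repeated measures could lower that SD and raise every power figure, without changing the relative loss. The tests remain weak either way, and the primary analysis and its conclusion are untouched.

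The case does not extend with the same force to BMI. The cut at 30 is a recognised clinical category and does not depend on the sample, so it may stay as planned.

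**What to change.** In the repeated-measures model under Analysis methods, enter age and symptom duration as continuous modifiers, each through a group × week × modifier term with its lower-order terms. Report the week-12 group × modifier contrast with its 95% CI as the test of effect modification. Keep the median splits only to display subgroup estimates, and leave the obesity category unchanged.

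The cost is a sentence or two in the SAP and no new data. The downside is a linearity assumption and, if duration is skewed, leverage from a few women with long-standing symptoms. Both can be checked, for example by repeating the duration analysis on the log scale. The report should also say that a non-significant interaction at this sample size is not evidence of a uniform effect.
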